2 STUDY OBJECTIVES

The objective of this phase 2 basket study is to evaluate the efficacy and safety of copanlisib in combination with fulvestrant administered to subjects with selected ER+ and/or PR+ advanced or metastatic solid tumors with PI3K and/or PTEN alterations

2.1 Part 1: Dose confirmation:

Primary Objective:

- To evaluate the safety, tolerability, and DLTs of copanlisib 60 mg administered IV on Days 1, 8 and 15 in combination with fulvestrant 500 mg administered IM on Day 1 and Day 15 of Cycle 1, and then on Day 1 of each subsequent 28-day cycle to confirm the RP2D of the combination therapy.

Secondary objectives:

- To assess the efficacy of copanlisib administered in combination with fulvestrant as outlined in Part 2 by evaluating the ORR.
- To evaluate additional efficacy measures such as PFS and OS of copanlisib in combination with fulvestrant.

Exploratory Objective:

- To investigate clonal evolution, and mechanisms of resistance using tissue and liquid biopsies utilizing ctDNA as outlined in Part 2.

2.2 Part 2: Dose expansion:

Primary objective:

- To assess the efficacy of copanlisib administered in combination with fulvestrant as outlined above by evaluating the ORR. Patients enrolled for Part 1 will be included in this efficacy analysis.

Secondary Objectives:

- To evaluate additional efficacy measures such as PFS and OS of copanlisib in combination with fulvestrant.
- To evaluate the safety and tolerability of copanlisib in combination with fulvestrant.

Exploratory Objective:

- To investigate clonal evolution, and mechanisms of resistance using tissue and liquid biopsies utilizing ctDNA.

Proprietary Information of MD Anderson

Protocol 2020-1241

19 October 2022

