4.1.4 Follow-Up Visits

Patients who discontinue study treatment for a reason other than disease progression will move into the follow-up phase. Patients will be monitored for disease status by tumor imaging (CT scan or MRI, as appropriate) every 8 weeks (± 7 days) until PD, death, initiation of new anticancer therapy, withdrawal of consent, or lost to follow-up.

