5 STUDY POPULATION

5.1 Patient Population

The study population will consist of subjects with selected HR+ (ER+ or/and PR+) advanced or metastatic solid tumors with PI3K (*PIK3CA*, *PIK3R1*) and/or *PTEN* alterations. Patients must have no available standard therapy known to prolong survival or are not candidates for such a therapy.

[figure not shown]

Proprietary Information of MD Anderson

Protocol 2020-1241

19 October 2022

all patients complete the first 28 days, the study will advance to Part 2 (dose expansion), provided there is no more than 1 DLT observed. Patients will be considered evaluable for Part 1 once they have completed at least 1 cycle of treatment or they experience DLTs in the first treatment cycle.

[figure not shown]

Cohort 1: Ovarian cancer (ER+ and/or PR+, PI3K or PTEN altered).

Cohort 2: Endometrial cancer (ER+ and/or PR+, PI3K or PTEN altered).

Cohort 3: Breast cancer (ER+ and/or PR+, PI3K or PTEN altered). Cohort 3 will be enriched to include at least 7 patients naïve to any PI3Ki in Stage 1 and also in Stage 2.

Patients will be considered evaluable for Part 2 once they have completed at least 2 cycles of treatment and have at least one efficacy assessment.

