8.1 Safety Analysis

All patients who received at least 1 dose of both copanlisib and fulvestrant will be included in a descriptive safety analysis. The safety profiles will be assessed through summaries of AEs, serious AEs, AEs leading to treatment discontinuation, and treatment-related death. The safety analysis will report the frequency, severity, and duration of all treatment related AEs and laboratory abnormalities, dose interruptions, dose reductions, and toxicity-related treatment discontinuation. The worst per-patient toxicity according to NCI CTCAE grade will be used. The Bayesian Beta-Binomial model will be used to quantify the statistical inference of AE rates.

The **MDACC IND Office Medical and Safety Group** will be provided with a copy of the safety and efficacy analysis when available.

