8.2 Efficacy Analysis

The ORR is defined as the proportion of patients who achieve CR or PR by the combination therapy per RECIST 1.1. Bayesian beta-binomial model and the CBHM will be used to model the data observed within each cohort. Bayesian 95% credible interval will be derived. Summary statistics will be given for secondary efficacy endpoints without borrowing information across cohorts. Time-to-event methodology will be used to assess mortality outcomes. Specifically, a log-rank statistic (accompanied by a Kaplan-Meier plot) will be the primary method of analysis for the mortality endpoint. Model-based methods (e.g., Cox proportional hazards or other robust methods) may also be applied.

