- e) AEs will be captured from the time of informed consent signing through 30 days after the last dose of study drug or initiation of a new anticancer therapy, whichever comes first.

- f) All concomitant medication received within 28 days prior to study drug initiation and 30 days after the last dose of study drug will be recorded, including all prescription, over-the-counter, IV medications and fluids, supportive care drugs and the drugs used to treat AEs or chronic diseases, and non-drug supportive interventions. If changes occur during the study period, documentation of drug dosage, frequency, route, and date will also be recorded.
- g) Archival tissue will be collected if available.
- h) Radiographic tumor assessments, using CT scanning or MRI, will be performed at Screening, Cycle 3 Day 1 (± 7 days), Day 1 (± 7 days) of every 2nd cycle after that, and at EOT.
- i) Patients who discontinue study treatment for a reason other than disease progression will move into follow-up phase. Patients will be monitored for disease status by tumor imaging (CT scan or MRI, as appropriate) every 8 weeks (± 7 days) until PD, death, initiation of new anticancer therapy, withdrawal of consent, or lost to follow-up.
- j) Copanlisib (60 mg IV) will be administered on Day 1, Day 8, and Day 15 of 28-day cycles until disease progression, unacceptable toxicity, death, withdrawal of consent, or discontinuation from the study drug for any other reason.
- k) Fulvestrant (500 mg IM) will be administered on Day 1 and Day 15 of Cycle 1 and only Day 1 of any subsequent 28-day cycle.
- l) Physical examination, performance status, vital signs and weight at baseline, weekly (D1, D8, D15, D22) during Cycle 1, twice during cycle 2 (D1 and D15), and then at the start of every cycle thereafter (within 3 days prior to treatment), or more frequently if clinically indicated. Finally at EOT/Progression.
- m) On copanlisib infusion days, blood pressure should be measured pre-dose, mid-infusion, end of infusion, and 1 and 2 hours after the end of infusion. Note: a window of ± 10 minutes is allowed for all BP measurements, except for pre-dose (0 hour) measurement
- n) MUGA scan or ECHO will be performed at screening and as clinically indicated. The same method should be used throughout the study.

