For equivocal findings of progression (e.g., very small and uncertain new lesions; cystic changes or necrosis in existing lesions), treatment may continue until the next scheduled assessment. If at the next scheduled assessment, progression is confirmed, the date of progression should be the earlier date when

Proprietary Information of MD Anderson

Protocol 2020-1241

19 October 2022

progression was suspected.

Stable Disease (SD): Neither sufficient shrinkage to qualify for PR, nor sufficient increase to qualify for PD, taking as reference the smallest sum diameters while on study.

Not Evaluable (NE): When an incomplete radiographical assessment of target lesions is performed or there is a change in the method of measurement from baseline that impacts the ability to make a reliable evaluation of response.

Evaluation of Non-Target Lesions

Complete Response: Disappearance of all non-target lesions and normalization of tumor marker level. All lymph nodes must be non-pathological or normal in size (<10 mm short axis).

Non-CR/Non-PD: Persistence of 1 or more non-target lesions and/or maintenance of tumor marker level above the normal limits.

PD: Unequivocal progression of existing non-target lesions. The appearance of 1 or more new lesions is also considered progression.

NE: When a change in method of measurement from baseline occurs and impacts the ability to make a reliable evaluation of response.

Evaluation of Best Overall Response

The best overall response (BOR) is the best response recorded from the start of the study treatment until the earliest of objective progression or initiation of new anticancer therapy, taking into account any requirement for confirmation. The patient's BOR assignment will depend on the findings of both target and non-target disease and will also take into consideration the appearance of new lesions. The BOR will be calculated via an algorithm using the assessment responses provided by the investigator over the course of the study.

Time Point Response

It is assumed that at each protocol-specified time point, a response assessment occurs. (When no imaging/measurement is conducted/made at all at a particular time point, the patient is NE at that time point.) **Table 21** provides a summary of the overall response status calculation at each time point for patients who have measurable disease at baseline.

Table 21: Time Point Response: Patients with Target (\pm Non-target) Disease

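### The Part 2 evaluability rule has no clause for early failures; if it sets the primary ORR denominator, patients who fail before two cycles drop out and ORR is biased upward

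*Combined protocol and SAP*

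**What the plan says.** Section 2.2 makes ORR the primary objective of Part 2 and adds: "Patients enrolled for Part 1 will be included in this efficacy analysis".

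The evaluability rules are in Section 5, in the text under 5.1. For Part 2, patients are "evaluable for Part 2 once they have completed at least 2 cycles of treatment and have at least one efficacy assessment". For Part 1, they are "evaluable for Part 1 once they have completed at least 1 cycle of treatment or they experience DLTs in the first treatment cycle".

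Section 8.2 gives the endpoint: "The ORR is defined as the proportion of patients who achieve CR or PR by the combination therapy per RECIST 1.1". Section 3.1 is similar. Neither says which patients form the denominator. The only analysis set named in the visible part of Section 8 is for safety (8.1): "All patients who received at least 1 dose of both copanlisib and fulvestrant will be included in a descriptive safety analysis".

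Imaging is scheduled in Appendix A, footnote h, at "Screening, Cycle 3 Day 1 (± 7 days), Day 1 (± 7 days) of every 2nd cycle after that, and at EOT". Section 4.1.4 covers those who stop early: "Patients who discontinue study treatment for a reason other than disease progression will move into the follow-up phase"; they are then imaged every 8 weeks. Appendix B adds: "When no imaging/measurement is conducted/made at all at a particular time point, the patient is NE at that time point".

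**The concern.** The Part 2 rule joins its two conditions with "and" and offers no alternative. A patient who dies, or who stops for progression or toxicity, before completing two 28-day cycles never becomes evaluable. That holds even if progression is documented on the end-of-treatment scan, because the scan meets only one of the two conditions. The Part 1 rule, in the same section, does keep patients who fail early with a DLT.

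If the Part 2 rule sets the primary denominator, membership of the analysis set is decided by a post-baseline outcome related to the endpoint. Early deaths and early progressors are almost certainly non-responders, so removing them raises ORR. No control arm is described that could show or offset the shift. ORR also feeds the cohort-level beta-binomial model and the calibrated Bayesian hierarchical model (CBHM), so the same selection would carry into both.

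**Working it through.** **Who is lost and who is kept under the Part 2 rule**

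- Lost: patients who die, or stop for progression or toxicity, before completing two cycles.
- Kept: patients whose progression is first seen at the Cycle 3 Day 1 scan, and patients who progress earlier but continue through two cycles, which Section 4.1.7 permits.
- Lost from numerator and denominator: any patient who stops early for toxicity and responds during the 8-weekly follow-up imaging. Appendix B requires a confirmatory assessment about 4 weeks after response criteria are first met, so such patients should be few, but the number need not be zero.

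**Part 1 against Part 2.** Section 2.2 brings in everyone enrolled for Part 1, with no two-cycle condition. Read literally, a Part 1 patient who stops in Cycle 1 for a DLT counts in ORR, and a Part 2 patient who stops for the same event does not.

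**Size.** The visible documents give no sample size, null or target ORR, decision cut-off or early-failure rate, so there is no stated figure to reproduce. Every input below is an assumption.

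Let p be the true ORR in all treated patients, d the fraction excluded and q the response rate among the excluded. Then

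apparent ORR = (p − d·q) / (1 − d).

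With p = 20%, d = 20%, q = 0: 0.20 / 0.80 = 25.0%. With q = 10%, half the overall rate: (0.20 − 0.02) / 0.80 = 22.5%.

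| True ORR | Excluded respond | d = 10% | d = 20% | d = 30% |
|---|---|---|---|---|
| 20% | never | 22.2% | 25.0% | 28.6% |
| 20% | at half the overall rate | 21.1% | 22.5% | 24.3% |
| 10% | never | 11.1% | 12.5% | 14.3% |
| 10% | at half the overall rate | 10.6% | 11.3% | 12.1% |

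In patient counts: 25 treated, 5 failing before two cycles, 4 responders all among those kept. ORR is 4/25 = 16% in all treated and 4/20 = 20% in evaluable patients.

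**Effect on a decision.** Take an illustrative single-look rule with p0 = 10%. It is not the trial's CBHM rule.

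- A: 25 evaluable patients with the excluded replaced, success at 5 or more responses. P = 1 − BinomCDF(4; 25, apparent ORR).
- B: 25 treated, no replacement, success at a fixed count of 5 or more. P = 1 − BinomCDF(4; 25, p0 − d·q).
- C: 25 treated, no replacement, success at an observed ORR of 20% or more, averaged over evaluable n ~ Binomial(25, 1 − d).

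With no exclusions each gives 9.8%.

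| Rule | Excluded respond | d = 10% | d = 20% | d = 30% |
|---|---|---|---|---|
| A | never | 13.7% | 19.5% | 28.1% |
| A | at half rate | 11.7% | 14.3% | 18.0% |
| B | never | 9.8% | 9.8% | 9.8% |
| B | at half rate | 8.3% | 6.9% | 5.6% |
| C | never | 10.9% | 17.2% | 25.7% |
| C | at half rate | 9.2% | 12.9% | 17.5% |
| C | at the overall rate (no selection) | 7.7% | 9.2% | 10.6% |

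The upward shift in ORR appears in every scenario where the excluded respond less often. Inflation of the false-positive rate does not: it depends on the decision rule and on replacement.

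**The case against.** The strongest objection is that the deciding text may exist but cannot be read. By the contents list, Section 8 starts on page 63 and Section 8.1 on page 67, and nearly all of what lies between is not shown. Section 5.2 is not visible either. An efficacy set, a replacement rule or the Stage 1 rule could be there, and text not shown cannot be treated as absent from the plan. This stands. It is why the conclusion is conditional, and why the weight rests on a rule that is written down rather than on a missing definition.

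Second, the visible ORR definitions say patients, not evaluable patients, and evaluability could serve another purpose, such as deciding when a patient counts toward a stage look. That is possible. But ORR is the only Part 2 primary objective and the rule requires an efficacy assessment, so the denominator is its most natural use. If the literal reading is intended, Section 5 still needs a sentence saying so.

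Third, a DLT is the endpoint of the Part 1 rule, so keeping DLT patients there is unsurprising, and Section 2.2 may be only a pooling statement. Fair: the contrast shows an unreconciled difference, not proof of intent. Likewise, the Appendix B sentence on patients without imaging defines a time-point status. It does not itself remove anyone from the denominator, though no visible sentence counts such patients as non-responders.

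Fourth, the largest false-positive figures require replacement of excluded patients, and the only visible replacement provision concerns allergic reactions, in the DLT definition. Correct: those figures show sensitivity to the rule and are not estimates for this trial.

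**Conclusion.** The concern holds as a conditional finding and should be fixed, with medium confidence. The missing early-failure clause is a fact of the visible text, and so is the lack of reconciliation between Section 5 and Sections 2.2, 3.1 and 8.2. The upward bias follows if the Part 2 rule sets the primary denominator and excluded patients respond less often than retained ones. The second condition is near-certain for early death or progression and less certain for early toxicity stoppers.

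Under the assumed exclusion fractions of 10% to 30%, a true ORR of 20% is overstated by about 1 to 9 percentage points (21.1% to 28.6%), and a true 10% by about 1 to 4 points (10.6% to 14.3%). The actual size cannot be derived from the documents. The effect on go/no-go decisions and on CBHM borrowing is undetermined, because the cut-offs and calibration settings are not shown.

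**What to change.** - In Section 8.2, define the primary ORR set as all Part 1 and Part 2 patients who received at least one dose of study treatment. Section 8.1 requires a dose of both drugs; since both are scheduled on Cycle 1 Day 1 the difference should be minor, but one wording should be used.
- Count as a non-responder anyone without a documented qualifying response, including patients with no post-baseline scan, only not-evaluable assessments, or fewer than two cycles. A qualifying response documented after early stopping counts as a response.
- Use this set at the Stage 1 look and in the CBHM.
- Keep the two-cycle evaluable set as a labelled sensitivity analysis.
- Reconcile Section 5 with Sections 2.2, 3.1 and 8. If the part of Section 8 not shown already defines such a set, a cross-reference from Section 5 is enough.

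The cost is wording in Sections 5 and 8; no new patients, visits or data are needed. The reported ORR may be somewhat lower. If stage sizes or the CBHM operating characteristics were set on evaluable patients, check that they still apply.

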5.3 Inclusion Criteria

Patients eligible for inclusion in this study have to meet all of the following criteria:

1. Histologically confirmed ER+ and/or PR+ advanced or metastatic solid cancer including ovarian cancer (cohort 1), endometrial cancer (cohort 2), or breast cancer (cohort 3). Cohort 3 will be enriched to include at least 7 patients naïve to any PI3Ki in Stage 1 and also in Stage 2. ER and/or PR positivity is defined as >10% immunohistochemical staining of any intensity.
2. Presence of one or more PI3K and/or PTEN alterations in tumor tissue. Genetic alterations will include *PIK3CA* gain of function mutations, *PIK3R1* loss of function mutations, *PTEN* loss of function mutations, and *PTEN* deletions.
3. Measurable disease per RECIST 1.1.
4. The patient (or legally acceptable representative, if applicable) provides written informed consent for the study.
5. Female or male ≥ 18 years of age on the day of informed consent signing.

Proprietary Information of MD Anderson

Protocol 2020-1241

19 October 2022

6. Patients have no available standard therapy known to prolong survival. For cohort 3 prior treatment with a PI3Ki and everolimus is not required. The patients with or without prior treatment with PI3Ki and everolimus will qualify for enrollment
7. Adequate archived tumor tissue for the analysis for PI3K and PTEN alterations if available.
8. ECOG performance status of ≤ 2 .
9. Adequate organ and marrow function as defined below:
 - a. Hemoglobin ≥ 9.0 g/dL
 - b. Absolute neutrophil count $\geq 1.5 \times 10^9$ /L
 - c. Platelet count $\geq 100 \times 10^9$ /L
 - d. TB $\leq 1.5 \times$ institutional ULN; Patients with known Gilbert's disease who have TB $\leq 3 \times$ ULN may be enrolled)
 - e. AST/ ALT $\leq 3 \times$ ULN. If patient has liver metastases, AST and ALT $\leq 5.0 \times$ ULN.
 - f. Creatinine $\leq 1.5 \times$ ULN
 - g. International normalized ratio ≤ 1.5 .
10. Fasting blood glucose ≤ 140 mg/dL and hemoglobin A1c $\leq 8.5\%$ (both criteria have to be met).
11. Cardiac ejection fraction $\geq 45\%$.
12. Women of childbearing potential must have a negative serum or urine pregnancy test (minimum sensitivity 25 IU/L or equivalent units of human chorionic gonadotropin [HCG]) within 14 days prior to the initiation of treatment and/or postmenopausal women must be amenorrheic for at least 12 months to be considered of non-childbearing potential. Women of childbearing potential (WOCBP) must agree and commit to the use of 2 highly effective methods of birth control throughout the duration of the study until at least 4 months following the last dose of study drug. Acceptable methods are defined as those that result, alone or in combination, in a low failure rate (i.e., less than 1% per year) when used consistently and correctly, such as surgical sterilization, an intrauterine device, or hormonal contraception in combination with a barrier method. Women using systemically acting hormonal contraceptives should add a barrier method. In certain countries (if permitted by law), WOCBP may agree to abide by heterosexual sexual abstinence during the time of participation in this study.
13. Male patients and their female partners of childbearing potential must agree and commit to use a barrier contraception (eg, condom with spermicidal foam/gel/film/cream/suppository) throughout the duration of the study until at least 60 days following the last dose of study drug, in addition to their female partners using either an intrauterine device or hormonal contraception and continuing until at least 4 months following the last dose of study drug. This criterion may be waived for male patients who have had a vasectomy > 6 months before signing the ICF.
14. Willing and able to comply with the protocol for the duration of the study, including undergoing treatment and scheduled visits and examinations.

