	
d. Total bilirubin (TB) $\leq 1.5 \times$ institutional upper limit of normal (ULN); Patients with known Gilbert's disease who have TB $\leq 3 \times$ ULN may be enrolled)e. Aspartate transaminase (AST)/ alanine transaminase (ALT) $\leq 3 \times$ ULN. If patient has liver metastases, AST and ALT $\leq 5.0 \times$ ULN.f. Creatinine $\leq 1.5 \times$ ULNg. International normalized ratio ≤ 1.5. 
10. Fasting blood glucose ≤ 140 mg/dL and hemoglobin A1c $\leq 8.5\%$ (both criteria have to be met).
 
11. Cardiac ejection fraction $\geq 45\%$.
 
12. Women of childbearing potential must have a negative serum or urine pregnancy test (minimum sensitivity 25 IU/L or equivalent units of human chorionic gonadotropin [HCG]) within 14 days prior to the initiation of treatment and/or postmenopausal women must be amenorrheic for at least 12 months to be considered of non-childbearing potential. Women of childbearing potential (WOCBP) must agree and commit to the use of 2 highly effective methods of birth control throughout the duration of the study until at least 150 days following the last dose of study drug. Acceptable methods are defined as those that result, alone or in combination, in a low failure rate (i.e., less than 1% per year) when used consistently and correctly, such as surgical sterilization, an intrauterine device, or hormonal contraception in combination with a barrier method. Women using systemically acting hormonal contraceptives should add a barrier method. In certain countries (if permitted by law), WOCBP may agree to abide by heterosexual sexual abstinence during the time of participation in this study.
 
13. Male patients and their female partners of childbearing potential must agree and commit to use a barrier contraception (eg, condom with spermicidal foam/gel/film/cream/suppository) throughout the duration of the study until at least 90 days following the last dose of study drug, in addition to their female partners using either an intrauterine device or hormonal contraception and continuing until at least 90 days following the last dose of study drug. This criterion may be waived for male patients who have had a vasectomy > 6 months before signing the ICF.
 
14. Willing and able to comply with the protocol for the duration of the study including undergoing treatment and scheduled visits and examinations.

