6.6 Contraception

Both copanlisib and fulvestrant can cause fetal harm during embryonic development. In pregnant animal models, the administration of copanlisib or fulvestrant caused embryo-fetal death and fetal abnormalities. No information is available on the safety of copanlisib or fulvestrant in pregnant human females. Neither copanlisib nor fulvestrant should be administered to pregnant

Proprietary Information of MD Anderson

Protocol 2020-1241

19 October 2022

women. Female patients of childbearing potential must either abstain from heterosexual intercourse or use a highly effective method of contraception for the course of the study through 150 days after the last dose of copanlisib or fulvestrant. Males with female partners of reproductive potential must abstain from sexual intercourse. Alternatively, they and their partners must use a highly effective method of contraception when engaging in sexual intercourse for the course of the study through 90 days after the last dose of copanlisib or fulvestrant.

Patients should be informed that taking the study medications may involve unknown risks to the fetus (unborn baby) if the pregnancy were to occur during the study. To participate in the study, they must adhere to the contraception requirement for the duration of the study and after the last day of treatment as described in the paragraph above. If there is any question that a patient will not reliably comply with the requirements for contraception, that patient should not be entered into the study.

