6.6.1 Female Patients

Women in the following categories are not considered women of childbearing potential:

- Premenopausal female with 1 of the following:
 - Documented tubal ligation
 - Documented hysterectomy
 - Documented bilateral salpingectomy
 - Documented bilateral oophorectomy
- Postmenopausal female
Postmenopausal is defined as ≥45 years of age, with at least 12 months of spontaneous amenorrhea.

Female patients of childbearing potential are eligible to participate if they agree to use a highly effective method of contraception consistently and correctly, as described in **Table 17** during the protocol-defined timeframe.

Table16: Highly Effective Contraception Methods

• Combined (estrogen and progestogen-containing) hormonal contraception
○ Oral○ Intravaginal○ Transdermal

• Progestogen-only hormonal contraception
○ Oral○ Injectable○ Implantable

• Intrauterine devices and intrauterine hormone-releasing system

• Bilateral tubal occlusion (women)

Proprietary Information of MD Anderson

Protocol 2020-1241

19 October 2022

- Vasectomized partner

A vasectomized partner is a highly effective contraception method provided that the partner is the sole male sexual partner of the woman of childbearing potential and the absence of sperm has been confirmed. If not, an additional highly effective method of contraception should be used.

- Sexual abstinence (men and women)

Sexual abstinence is considered a highly effective method only if defined as refraining from heterosexual intercourse during the entire period of risk associated with the study treatment. The reliability of sexual abstinence needs to be evaluated in relation to the duration of the study and the preferred and usual lifestyle of the patient. Periodic abstinence (such as a calendar, symptothermal and post-ovulation methods, withdrawal (coitus interruptus), and the lactational amenorrhea method are not acceptable methods of contraception

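### Contraception rules conflict: 5.3 gives different post-treatment periods from the synopsis and 6.6, and the synopsis and 5.3 ask women for two methods where 6.6 and 6.6.1 ask for one

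*Combined protocol and SAP*

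**What the plan says.** **Women of childbearing potential.** Criterion 12 in section 5.3 asks for "2 highly effective methods of birth control throughout the duration of the study until at least 4 months following the last dose". Criterion 12 in the synopsis (Key Inclusion Criteria) asks for "2 highly effective methods of birth control throughout the duration of the study until at least 150 days following the last dose". Section 6.6 gives women the choice of abstaining or being required to "use a highly effective method of contraception for the course of the study through 150 days after the last dose of copanlisib or fulvestrant". Section 6.6.1 words the requirement as an eligibility condition: "Female patients of childbearing potential are eligible to participate if they agree to use a highly effective method of contraception consistently and correctly".

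**Male patients and their partners.** Criterion 13 in section 5.3 requires barrier use "until at least 60 days following the last dose of study drug"; the synopsis requires it "until at least 90 days following the last dose of study drug, in addition to their female partners". For female partners, 5.3 asks for "either an intrauterine device or hormonal contraception and continuing until at least 4 months following the last dose of study drug", where the synopsis gives 90 days. Section 6.6 sets 90 days for men and their partners together. Section 6.6.2 adds a condom with spermicide for the man and a highly effective method for a partner who could conceive; it gives no period.

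**Pregnancy reporting.** Section 6.7 sets reporting windows of 150 days after the last dose for female patients and 90 days for partners of male patients.

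**The concern.** Section 6.6 states that both drugs can cause fetal harm, so the period after the last dose is a protective rule. Section 5.3 is the operative eligibility list, since every criterion in it has to be met, and cannot be set aside as summary text. A woman, or a man using a barrier, who follows 5.3 exactly and nothing else would stop before the period in 6.6 has ended.

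The number of methods raises a different problem. Criterion 12 in 5.3 and the sentence in 6.6.1 are both conditions for entry, and they ask for different commitments. Staff who work from one section would record a different agreement from staff who work from the other.

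**Working it through.** No sample size, power or error rate is involved, so the check sets the passages side by side and converts months to days.

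| Requirement | Synopsis | 5.3 | 6.6 |
|---|---|---|---|
| Women: period after last dose | 150 days | 4 months | 150 days |
| Male patients: barrier use | 90 days | 60 days | 90 days* |
| Female partners of male patients | 90 days | 4 months | 90 days* |
| Women: number of highly effective methods | 2 | 2 | 1 (also 6.6.1) |

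*Section 6.6 gives one period for men and their partners and does not name a barrier method there.

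**Conversion.** Four calendar months, counted from every start date in 2021 to 2024, last 120 to 123 days. For example, 1 February to 1 June in a non-leap year is 28 + 31 + 30 + 31 = 120, and 1 May to 1 September is 31 + 30 + 31 + 31 = 123.

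**Differences.**
- Women: 150 − 123 = 27 to 150 − 120 = 30 days shorter in 5.3 (27/150 = 18%; 30/150 = 20%).
- Male barrier use: 90 − 60 = 30 days shorter in 5.3 (30/90 = 33%).
- Female partners: 120 − 90 = 30 to 123 − 90 = 33 days longer in 5.3.

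The differences run in both directions, so neither rounding between months and days nor a uniformly stricter section explains them.

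**Where the split falls.** On periods, 5.3 stands against the synopsis and 6.6. On the number of methods for women, the synopsis and 5.3 stand together against 6.6 and 6.6.1. Correcting 5.3 to match the synopsis would therefore settle the periods but not the number of methods.

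**Secondary item: lowest copanlisib dose level.** Footnote a of Table 12 (blood pressure) and footnote a of Table 15 (pneumonitis) give 45 mg. Footnote b of Table 13 (skin) gives 30 mg. Against the 60 mg start these are 45/60 = 75% and 30/60 = 50%. If the levels are 60, 45 and 30 mg (an assumption, because the dose-level text in 6.2 is not visible), the floors allow one and two reductions respectively. No footnote says that its floor applies to one toxicity only.

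**The case against.** The strongest reply is that nobody is left without a compliant path. The periods in 5.3 and the synopsis are minimums, no passage forbids a longer period or an added method, and 6.6 makes participation conditional on its own requirement. A single commitment can satisfy every passage. This stands, and it limits the consequence. It does not remove the conflict, because a person held to 5.3 alone is not told of the longer period.

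On the number of methods, 5.3 itself softens the demand for two: "Acceptable methods are defined as those that result, alone or in combination, in a low failure rate". That makes 5.3 less clear; it does not bring it into line with 6.6.1.

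Few patients may be affected. Section 6.6.1 takes postmenopausal women and those with documented hysterectomy, bilateral oophorectomy, bilateral salpingectomy or tubal ligation out of the group. The rows for men can arise only in the breast cohort. The documents do not give the numbers.

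Three stronger readings are tempting, and the documents do not support them:
- A reader might infer that 5.3 contradicts 6.7. But 6.7 sets a reporting window, which may properly outlast a contraception minimum. Its match with the synopsis and 6.6 is supporting context only.
- A reader might infer that the number of methods also conflicts for men. But 6.6.2 asks for a condom with spermicide plus an effective method for the partner, which broadly matches criterion 13 in 5.3.
- A reader might infer that the 45 and 30 mg footnotes prove a wrong dose rule. Each sits under a toxicity-specific table. Table 13 allows two reductions and Table 15 one, which would fit separate floors on the assumed levels. The hidden text in 6.2 may define them.

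**Conclusion.** The contraception rules contradict each other in visible, current text, and the passages must be reconciled. Section 5.3 ends 27 to 30 days before the 6.6 period for women and 30 days before it for male barrier use, and runs 30 to 33 days beyond it for female partners. Women are asked for two methods in the synopsis and 5.3 and for one in 6.6 and 6.6.1. Confidence is high: the finding rests on no hidden figure, and the only conversion is from calendar months to days.

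The category is internal inconsistency, not a disputed design decision. The weight comes from participant protection and clear eligibility. No efficacy result is affected. The text does not show that any participant would be unprotected, since the consent form is not in the copy reviewed and 6.6 carries its own adherence condition.

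The dose-floor difference is real but separate and secondary. Confidence there is moderate, because the dose-level text in 6.2 is not visible.

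**What to change.** 1. Make the periods after the last dose agree across the synopsis, 5.3 and 6.6, for women, for male patients and for the female partners of male patients.
2. Make the number of methods for women agree across the synopsis, 5.3, 6.6 and 6.6.1.
3. Check the consent form against the result.
4. As a separate item, reconcile the footnotes to Tables 12, 13 and 15 on the lowest copanlisib dose level, or state that the floors are toxicity-specific.
5. Editorial: 6.6.1 and 6.6.2 send the reader to Table 17 for contraception methods. That is the adverse-event recording table; the methods are in Table 16.

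This review takes no view on which period, number of methods or dose floor is right; that is for the sponsor's clinical team. The cost is amendment wording and the consent-form check, with no effect on sample size or timeline.
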